COVER PAGE

Date/Version: January 25, 2017 / 3.0

Title of Protocol: The effect of MINGO (rice, mungo, moringa) as a nutritional supplement in patients with X-Linked Dystonia Parkinsonism (XDP) in Capiz, Philippines

Protocol Number: NCT03019458

Principal Investigator: [name].

Co-Investigators: None

Study Staff: MDSP members in the Philippines; Other healthcare providers and office staff, Sunshine Care Foundation staff and community advocates (CAs)

Background and Significance

X-linked dystonia parkinsonism (XDP, formerly known as DYT3) occurs primarily in Filipino males and is characterized by neurodegenerative dystonia and parkinsonism. It is currently recognized to have wide phenotypic variability relating to age of onset, location of disease onset and rate of severity/disease progression. Most patients begin with focal dystonia that generalizes with the development of parkinsonism later in disease course. XDP patients suffer from severe nutritional loss due to symptoms such as dysphagia, loss of appetite, and consistently high metabolic requirements brought about by their movement disorder. Approximately 79% of patients with XDP have experienced rapid weight loss since the onset of their disease. It is the aim of the researchers to assess the clinical usefulness of adding a nutritional supplement to the daily dietary needs of these patients.

MINGO is a supplement consisting of local ingredients such as moringa, rice and mung beans, which can be added to any type of edible paste, food, and liquid. Mingo has gained popularity as an emergency food in disaster relief operations due to the ease of its preparation, its high nutritional value and relatively low price. For the last two years, it has also been used as an agent for nutritional build up in malnourished populations of children. This study will provide valuable information on whether patients with XDP can increase their weight by consuming MINGO, which will lead to improvements in the patients' medical care and well-being.

Specific Aims

1. To determine the effect of the addition of MINGO on the following:
 - a. Patient body mass index (BMI)
 - b. Patient mid-upper arm circumference (MUAC)
2. Ensure that the addition of MINGO to diets of patients with XDP does not cause significant disturbance of baseline metabolic parameters, such as:
 - a. Uric acid
 - b. BUN
 - c. Creatinine
 - d. Potassium
 - e. A1C (tested in diabetic patients)

Research studies under this protocol will be conducted through:

- Subject recruitment and enrollment at:
 - The Health Centrum Hospital in Banica Roxas City
 - Local trips around the island of Panay and surrounding islands

Subject Selection

We will enroll any individual who meets the following eligibility criteria:

Inclusion:

- Patient is above the age of 18 years old
- Patients is diagnosed with XDP or a related movement disorder that often coexists with XDP by a neurologist with movement disorders training
- Patient has a "yes" response to the criteria "supportive home environment" in the patient's most recent "Doctor's monthly report"
- Patient meets the following accessibility criteria as determined by discussions with clinical staff:
 - a. Accessibility to the patient's home based on proximity from the research staff and availability of proper roads and public transportation

Exclusion:

- Patients who have movement abnormalities that have prevented the clinical staff to obtain an accurate height and weight measurement such as bed ridden or wheel chair bound patients
- Patients who have metabolic derangements prior to the study (i.e. creatinine twice the normal, A1C greater than 7) **and confirmed by physician's medical opinion**

- Patients who are taking pharmacological agents and medicinal supplements (i.e. agents other than what is considered to be part of the patient's standard care as determined by MDSP clinicians at the MDSP XDP clinic) that may affect weight
- Patients that report other medical conditions that can affect BMI such as hypo-, hyper-thyroidism, or history of malignancy
- Patients who have recently been hospitalized within the last 2 weeks from the start of the trial
- Patients who have a G-tube or NGT

Withdrawal Criteria:

- Subjects can stop a study visit or study procedure at any time
- Subjects can ask to have their data removed from analysis at any time
- The principal investigator can withdraw a subject during a study visit or procedure at any time for safety or noncompliance.

Source of subjects and recruitment methods

The study will use a convenience sample. Subjects are recruited through two sources.

1. The XDP Clinic and Registry at The Health Centrum Hospital in Banica Roxas City
2. Patient home visits by Sunshine Care Foundation employees

Remuneration

Subjects receive no remuneration for joining the study.

Subject Enrollment

There is no set limit to the number of individuals who can participate in the trial. The specific target population that the study will target is XDP patients who get care at the Health Centrum. The number will be determined by how many patients meet the inclusion/exclusion criteria.

Subject Prescreening

Subject prescreening consists of reviewing the medical records of patients with XDP seen at the Movement Disorders clinic in The Health Centrum in Roxas City. The researchers will identify patients who meet the eligibility criteria. Additionally, discussions with clinical staff will aid the researchers in determining whether the patient meets the accessibility criteria, such as the accessibility to the patient's home based on proximity from the research staff and availability of proper roads and public transportation. Eligible patients will be identified, contacted, and asked whether they are interested in participating in the study. An identifying prescreening log will be kept for all individuals screened.

Procedures for obtaining informed consent

Written consent is obtained from all subjects:

If the potential subject is unable to give consent due to physical condition, consent is obtained from the parents/legal guardian or spouse/next-of-kin.

For subjects physically incapable of signing the consent form due to their disease: These subjects retain the ability to understand the concepts of the study and to evaluate the risk and benefit of being in the study when it is explained verbally, and the individual is able to indicate approval or disapproval to study enrollment. The consent form will document the method used to communicate with the prospective subject and the specific means by which the prospective subject communicated agreement to participate in the study. An impartial third party will witness the entire consent process and sign the consent document.

In all cases, a copy signed by both the subject and study staff is placed in the subject's research file.

Enrollment of people within vulnerable groups

People with XDP have, at present, an incurable disease that often causes significant movement abnormalities such that men with XDP are prevented from returning to work. Thus, men with XDP typically use social assistance given their unemployment. Medical care through the XDP Clinic is provided free-of-charge (through the support of the Sunshine Foundation) to people diagnosed with XDP by a neurologist with movement disorder training. Verbally, and in the written consent form, we will clearly state that people with XDP can decline research participation and still receive medical care through the XDP Clinic. Medical care for people with XDP is NOT contingent on participation in research.

Study Procedures

a. Assessing Baseline Metabolic Parameters

Once informed consent has been obtained, enrolled patients will be tested for the following metabolic parameters: uric acid, BUN, creatinine, potassium, and, exclusively for diabetic patients, A1C. These tests will require at most 5mL of blood from patients. These values will be collected before the three-month period of MINGO consumption by the trial group to satisfy the lab value exclusion criteria.

b. Patient Randomization

Placement into the trial or control group will be randomly assigned. The trial group will receive and consume MINGO throughout the duration of the study while the control group will not. Both groups will undergo the same number of study visits, with the same data information collected.

c. Trial Group MINGO Consumption: Training and Requirements

The researchers will organize a training session before beginning the trial where study staff, namely the community advocates (CAs), will be trained on the correct preparation of MINGO, how many sachets are required of patients, how to prepare food logs, and how and when measurements will be taken. The study staff will then teach the patients and caregivers belonging to the trial group this information in their homes.

MINGO sachets can be consumed mixed with other food and liquid items and will not be used to replace regular meals. Caregivers will ensure intake of MINGO by the patient and study staff will collect the empty sachet bags every two weeks, as well as review food logs to ensure that MINGO is being consumed properly. Any report of non-compliance will be logged and participants will be withdrawn from the study once they are found to have missed more than six MINGO sachets per week.

d. Patient Data Collection Procedures

Each CA will be assigned a number of patients enrolled in the study. They will measure the weight of their group of patients for the entire duration of the study using a calibrated weight scale. The scale will be calibrated before every use (i.e. every two weeks). Each CA throughout the duration of the study will use the same scale. The CA will take weight measurements every two weeks at patient homes and a total of seven measurements will be done in three months.

Study staff will measure MUAC at the start of the study. MUAC measurements will be taken before the study, every four weeks, and at the end of the study.

At the end of the trial, the researchers may do multiple chart reviews in order to gather information on the patient's disease severity, caregiving, and family information.

Study Visits and Parameters to be Measured

Information that may be collected from/about subjects is listed on the:

- Data Collection Sheets
 - GUID information sheet: 10 identifying data elements for generating a Global Unique Identifier (GUID)
 - Movement disorder rating scales results from patient medical records
 - Burke-Fahn-Marsden Dystonia Scale (BFMDS)

- Unified Parkinson’s Disease Rating Scale (UPDRS)
 - XDP-MDSP Rating Scale
 - Swallowing assessments from patient medical records
 - MGH-SST
 - EAT-10
 - Caregiving scale and family information from patient medical records
 - Family APGAR
 - Modified Caregiver Strain Index (MCSI)
 - WHO-5 Index of Well being (WHO-5)
 - Trial participant sheet
 - Weight
 - Weight history
 - MUAC
 - Metabolic lab results
 - Demographic information from patient medical records
 - Patient education
 - Average annual income
- Food logs from caregivers and patients

Procedures

Phlebotomy

5 mL of blood from vein puncture may be used to obtain metabolic parameters on all subjects. The blood will be drawn by a professional trained in phlebotomy and will not be handled or collected by any of the study staff. A local lab that provides blood analysis for clinical use will be consulted.

Data Processing and Storage

Clinical data sheets will be labeled with the subject’s full name. At data entry, clinical data sheets will be checked for accuracy and completion. The subject’s Global Unique Identifier (GUID) will be generated. The GUID will be recorded on a code key corresponding to the subject’s name. No one at NeuroBANK™ will ever have access to the code key.

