COVER PAGE

Date/Version: November 11, 2016 / 1.2

Title of Protocol: The effect of MINGO (rice, mongo, moringa) as a nutritional supplement in patients with X-Linked Dystonia Parkinsonism (XDP) in Capiz, Philippines

Protocol Number: NCT03019458 Principal Investigator: [name].

Co-Investigators: None

Study Staff: MDSP members in the Philippines; Other healthcare providers and office staff, Sunshine

Care Foundation staff and community advocates (CAs)

Version 1.2 November 11, 2016

A linear mixed effects model will be used to determine if Mingo supplementation on top of regular diet would increase the BMI of XDP patients compared to regular diet alone. Baseline BMI, BFM scores, Eat 10 scores, and MGH SST scores, as fixed and random effects, will be incorporated into the model to adjust for their potential confounding effects. Data will be encoded in MS Excel 2007 and analyzed in R version 3.4.1, and using RStudio IDE, Version 1.0.153. All data will be analyzed by intention to treat.

Since this is a rare disease with a predefined number of 50, the study plans to have an acceptable power of 80% with the given limitation of 24 for the MINGO arm and 26 for the Control at the alpha level = 0.05. To achieve this power, we need to show an effect size of 2.23. The USCF Clinical and Translational Science Institute sample size calculator was used to find the effect size.

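### Patients who miss too many MINGO sachets leave the study unmeasured, and only the MINGO arm can trigger the rule; this does not fit the intention-to-treat analysis and may bias the MINGO effect

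*Protocol*

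**What the plan says.** **The rule.** Protocol, Study Procedures, c: "participants will be withdrawn from the study once they are found to have missed more than six MINGO sachets per week". Compliance is checked from food logs and returned packaging: "study staff will collect the empty sachet bags every two weeks". The same section says "Caregivers will ensure intake of MINGO by the patient".

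**Who is exposed to it.** Study Procedures, b: "The trial group will receive and consume MINGO throughout the duration of the study while the control group will not". The Addendum offers MINGO to controls only in an extension.

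**Other withdrawals.** Withdrawal Criteria: "The principal investigator can withdraw a subject during a study visit or procedure at any time for safety or noncompliance". This provision covers both arms and says nothing about later measurement.

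**Planned outcomes.** Study Procedures, d: for weight, "a total of seven measurements will be done in three months"; for arm circumference, "MUAC measurements will be taken before the study, every four weeks, and at the end of the study".

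**Analysis.** The SAP specifies a linear mixed effects model for BMI with baseline BMI, BFM, EAT-10 and MGH-SST scores, and adds "All data will be analyzed by intention to treat". It gives no rule for missing data or withdrawn patients.

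The number of sachets per week in the main trial is not stated. The Addendum mentions six intakes a day, for the extension only.

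**The concern.** Missing sachets is a post-randomisation event that controls cannot have. Removing such patients from the study ends their outcome data in one arm only. Background and Significance and Risks and Discomforts describe swallowing trouble, poor appetite and the strain of eating more. Any of these could cause both missed sachets and later weight loss. If so, the MINGO arm sheds patients who are doing badly, their counterparts stay in the control arm, and part of the estimated MINGO effect is selection. With 24 and 26 patients, a few one-sided losses can matter, and unmeasured visits cannot be recovered afterwards.

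**Working it through.** **1. The text.** The rule is mandatory, refers to the study rather than the supplement, and stands under the trial-group heading. No section of either document provides for weight or MUAC after withdrawal. The instruction to destroy data (Data and Sample Distribution) concerns subjects who ask to withdraw, not the sachet rule. The intention-to-treat statement therefore covers patients whose later outcomes the protocol stops collecting. The finding rests on this step; the figures below only show a possible size.

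**2. The plan's own figure, for scale.** The SAP gives an effect size of 2.23 for 24 v 26 at 80% power and alpha 0.05, with no unit or SD. Two-sided, the detectable difference is (1.960 + 0.842) × √(1/24 + 1/26) = 0.793 SD. As a raw difference, 2.23 implies SD = 2.23/0.793 = 2.81. That SD is not stated, so the figure can be neither confirmed nor refuted.

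**3. How often the rule might be met.** Assume n sachets a week, adherence p and independent misses over 12 weeks.
- Counted weekly: 1 − [1 − P(Bin(n, 1−p) > 6)]^12
- Averaged over each two-week collection: 1 − [1 − P(Bin(2n, 1−p) > 12)]^6

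Example, n = 42, p = 0.90: weekly probability 0.1214, so 1 − 0.8786^12 = 0.79.

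| Sachets per week | 14 | 21 | 28 | 42 |
|---|---|---|---|---|
| 95%, weekly | 0.0% | 0.1% | 0.4% | 5.3% |
| 90%, weekly | 0.2% | 3.9% | 19.5% | 78.9% |
| 90%, two-week | 0.0% | 0.1% | 1.8% | 37.0% |
| 85%, weekly | 2.6% | 29.5% | 77.0% | 99.9% |

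If all patients share one adherence rate, breaches are chance and cause no bias. Bias needs adherence to be related to weight change.

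**4. Bias for a fixed number withdrawn.** Simulation: 24 v 26, seven visits over weeks 0–12, no true effect. Assumed baseline BMI SD 2.5, week-12 change SD 0.8 (linear), residual SD 0.25. REML with random intercept and slope; arm, time, arm-by-time and a score unrelated to selection; t with 47 df; 2,000 replicates (SE of bias about 0.006). Correlation of adherence with BMI change 0.3 to 0.7:

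| | 5 of 24 withdrawn | 12 of 24 withdrawn |
|---|---|---|
| Last visit week 2 or 4: bias, kg/m² | 0.05–0.16 | 0.08–0.33 |
| – type I error | 5–12% | 5–23% |
| Last visits spread over weeks 2–10: bias, kg/m² | 0.03–0.07 | 0.04–0.12 |
| – type I error | 5–7% | 5–8% |

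At correlation 0, bias is about 0 and type I error 5%.

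**5. Bias when the rule itself decides who leaves and when.** Same model; mean adherence 90%, varying between patients (logit SD 1) and constant over time; last visit is the two-weekly review that finds the breach.

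| Sachets per week | 14 | 21 | 28 | 42 |
|---|---|---|---|---|
| Weekly count: patients of 24 losing visits | 1.6 | 4.0 | 6.4 | 10.4 |
| – bias, correlation 0.3 | 0.02 | 0.03 | 0.06 | 0.10 |
| – bias, correlation 0.7 | 0.04 | 0.10 | 0.15 | 0.24 |
| – type I error, correlation 0.7 | 4% | 6% | 9% | 15% |
| Two-week average: patients losing visits | 0.8 | 2.4 | 4.3 | 7.9 |
| – bias, correlation 0.7 | 0.02 | 0.08 | 0.11 | 0.20 |

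Repeat simulations at correlation 0.7, weekly count, gave closely similar bias at 14, 28 and 42 sachets. Their type I error was somewhat lower: about 7% at 28 and 12% at 42. With mean adherence 95% or 85% (weekly, correlation 0.7), bias is 0.01–0.09 or 0.09–0.33. At 7 sachets a week the rule requires missing all of them: about 0.04 of 24 patients lose visits, and bias is 0.007 (SE 0.006), that is, none.

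**6. Follow-up continued for all.** At correlation 0.7, bias is −0.001 and type I error 5.0%.

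**The case against.** **A mixed model using every available visit in the randomised arm is commonly called intention to treat and is valid under missing at random.** Visits before withdrawal do stay in, so the gap is the later outcomes. But the assumption must hold given what the model contains, and adherence is not in it.

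**The model adjusts for baseline swallowing and dystonia scores, the likely reasons for missed sachets.** This helps only if the scores may alter the weight trajectory. With selection wholly through a measured score (correlation 0.5, cut-off after week 2, 6 or 12 withdrawn), bias was 0.130 or 0.232 with the score as a main effect and 0.004 in both cases with score-by-time. The SAP's description of the scores as both fixed and random effects does not settle which is meant.

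**The protocol plans equal visits in both groups and weights throughout the study.** Neither statement mentions withdrawn patients. If they were meant to be included, that would contradict removal from the study, which is a further reason to reconcile the text.

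**The bias may be trivial.** This stands. The largest values need a strong correlation with either early loss of half the arm or 85% adherence at 42 sachets a week, a count taken from the extension. Caregiver supervision, the requirement for a home judged supportive, and the exclusion of tube-fed and bedridden patients lower the risk further. None of these restores a lost visit.

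**Conclusion.** The concern holds on the text: a mandatory withdrawal from the study that only the MINGO arm can trigger, with no later measurement, does not fit the declared analysis. Bias is possible, not certain, and would probably favour MINGO. If 2.23 is in kg/m², the largest simulated bias is 0.33/2.23 = 15% of it. Every simulated size rests on assumed sachet number, adherence, SDs, correlation and timing. Persistent low adherers breach early (median last visit week 2–6 in step 5), whereas later falls in adherence resemble the spread case. The documents also leave open whether the threshold applies to any single week or to an average.

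**What to change.** In Withdrawal Criteria and Study Procedures, c, separate stopping MINGO from leaving the study, and add: *A patient who meets the sachet rule, or is withdrawn for noncompliance, still has all remaining planned weight and MUAC measurements, unless the subject declines, and is analysed in the randomised arm.* Whether the threshold ends MINGO intake is for the investigator; this change leaves it alone.

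In the SAP, report withdrawals by arm and reason. Optional: a sensitivity analysis for remaining dropout with EAT-10-by-time, MGH-SST-by-time and BFM-by-time terms, and a secondary per-protocol set using the threshold.

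The cost is a short protocol amendment and two SAP sentences. The SAP (version 1.2, November 2016) predates the protocol (version 3.0, January 2017), so the two need aligning anyway. The home visits are already scheduled.

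The estimate will then include non-adherent patients, as intention to treat requires. If MINGO had no effect in a share w of 10%, 20% or 30%, a true difference of 2.23 would become 2.23 × (1 − w) = 2.01, 1.78 or 1.56. Power in a simple two-group comparison with SD 2.81 would be 71%, 61% or 50%.

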If a study participant is injured during the course of the study, appropriate measures will be implemented. Members of the study staff will meet as a team, investigate the details of the injury further, inform the IRB, and notify the current medical team, including the patient's general practitioner and medical staff at the XDP Movement Disorders clinic in Roxas City. The staff may not offer the patient the care needed to treat any injury that directly results from taking part in this research study. The staff will encourage the patient to bill the insurance company or other third parties, if appropriate, for the care they may get for the injury. There are no plans to pay the patient or give the patient other compensation for an injury, should one occur.

Publishing Rights:

The following individuals will have the authorship right to publish the results of the study for the direct or indirect role in seeing this project through: [name], [name], [name], [name], [name], [name], [name], [name], and [name] (if he is still with us for the duration of the study). We will also give an acknowledgement to the Health Centrum and the Sunshine Care Foundation for the support that was given.

Addendum to MINGO protocol:

For the control patients that will receive MINGO as part of their participation in the MINGO trial, we will ask them if they would like to participate in MINGO extension. In the extension, we will ask them if they are willing to take MINGO 6 times a day and undergo measurements similar to the original experimental group. That is, a writing a weekly food log, bimonthly weight measurements, and monthly Mid Upper Arm Circumference.
